#### 2. Stimulation Visit

The second visit includes completion of the full informed consent form and urodynamic testing with and without stimulation. This visit will be conducted within 4 weeks of the Screening and Enrollment Visit. This visit will be conducted in the clinic/site in person. Before any additional study activities occur, the full study consent form must be completed. Prior to beginning the UDT, a urinalysis will be performed to screen for a UTI and a urine pregnancy test will be performed. Before UDT begins, a prophylactic antibiotic will be administered to the patient to prevent urinary tract infection (UTI). In this visit the neuromodulation settings of the implanted device will be adjusted to deliver acute simulation. At the end of the UDT the settings will be

returned to the previously set therapeutic values. The neuromodulation settings constitute the "dose" and can include the voltage/current amplitude, frequency, pulse width, on time/off time duration and electrode polarity assignments. These parameters are limited by the available ranges of the approved neurostimulation device and will be adjusted during the study by the principal investigator to stay within the safe and comfortable levels for each individual study subject.

3.

The following information will be collected during this visit:

- Stimulation previous and current properties/setting
- Urethral Pressure Profile
- UDT data, including Leak Point Pressure (LPP) with and without stimulation
- Complications

Inspire Medical Systems, Inc. is collaborating with Beaumont on this study. Inspire hopes to use insight gained from this trial to guide the creation of a new implantable neurostimulator for patients with stress and mixed incontinence. We have a data sharing agreement in place with Inspire. They are not the study sponsor. They have provided funding for the study to take place and will receive de-identified results. They may wish to be present at some, or all, of the UDT visits. They may attend in person or remotely, via audio headsets. Their presence at these visits would serve to provide real-time feedback and suggestions to study staff. Participants will have the right to decide whether or not representatives from Inspire may be present at their UDT visit.

The purpose of real-time collaboration between study staff and Inspire is to make decisions about the best time points and/or bladder volumes to stop for leak point pressure testing, and whether leak point pressure testing should be repeated with stimulation off if no leaks are elicited with stimulation off. The representatives from Inspire may provide additional guidance, as needed, for troubleshooting and ensuring no important data collection is missed.

4. Follow-Up Phone Call

The third visit will take place by phone and will include assessment of any adverse events which may develop following the Stimulation Visit. This will take place 1 week (+/- 2 days) after the Stimulation visit.

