#### 5.2 Primary Endpoints

1. Identification of all study-related adverse events
2. Measurement of the changes in LPP with acute PNS compared to without stimulation

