### 7.3 Determine Leak Point Pressure Without and With Stimulation

7.3.1 Move the subject into a sitting or other position as per clinician.

7.3.2 Ensure acute stimulation parameters are set as determined in 7.1.4, above, so that the stimulation pulse train will be delivered continuously when manually turned on. The stimulation will be manually turned off for the infusion delivery periods.

7.3.3 Adjust the urodynamic system to infuse saline at 50 mL, 100mL or increments per investigator at a 50 mL/min infusion rate per physician's discretion.

7.3.4 Start the urodynamic saline infusion into the bladder until the first volume is reached (recommended at either 50mL, 100mL or per investigator) and pause the infusion.

7.3.5 Observe for urinary leakage while patient performs one or more coughs or Valsalva maneuvers with stimulation off to assess LPP.

7.3.6 Turn on stimulation per 7.1.4 and repeat the LPP assessment, using one or more coughs or Valsalva maneuvers as confirmation. Turn off stimulation. Note: This step may be omitted if no leak is observed in 7.3.5 or per physician's discretion.

7.3.7 Continue the urodynamic saline infusion (end the infusion pause mode) and fill the bladder to the next assessment point and stop infusion. Repeat the LPP with stimulation off, and then with stimulation on per 7.3.5 above 7.3.6.

7.3.8 Continue performing Valsalva and forceful coughs at additional bladder volume intervals without and with stimulation (steps) until patient has strong desire to void, bladder reaches major detrusor instability, patient has significant leakage (more than drops), patient has discomfort or any other reason per PI.

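### Repeating dry stimulation-off tests without matching stimulation-on attempts can make stimulation look better with no true effect

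*Combined protocol and SAP*

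**What the plan says.** The second primary endpoint in 5.2 is "Measurement of the changes in LPP with acute PNS compared to without stimulation". It is a within-subject comparison of stimulation on (ON) with stimulation off (OFF).

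Four places govern how many attempts each state gets:

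- **6.3, Stimulation Visit.** The funder may attend: "Their presence at these visits would serve to provide real-time feedback and suggestions to study staff". The stated purpose is to "make decisions about the best time points and/or bladder volumes to stop for leak point pressure testing" and to settle "whether leak point pressure testing should be repeated with stimulation off if no leaks are elicited with stimulation off". Of the funder the same section says "They have provided funding for the study to take place and will receive de-identified results", and also "Inspire hopes to use insight gained from this trial to guide the creation of a new implantable neurostimulator". Attendance is subject to consent: "Participants will have the right to decide whether or not representatives from Inspire may be present at their UDT visit".
- **7.3.5 to 7.3.7.** At each volume OFF comes first, with one or more coughs or Valsalva manoeuvres. ON follows: "Repeat the LPP with stimulation off, and then with stimulation on per 7.3.5 above 7.3.6". The note to 7.3.6 allows the ON step to be left out when OFF was dry, or at the physician's discretion.
- **7.3, note C.** Assessments in either state may be repeated at the investigator's discretion. There is no trigger, no cap and no requirement of equal numbers.
- **10 and 10.1.** The analysis is descriptive. It does not say which of several attempts enters the LPP comparison, or how dry tests and omitted ON tests are handled.

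**The concern.** The only repeat trigger that the plan names is a dry OFF test. Each further OFF attempt is another chance to leak, and no passage obliges staff to give ON the same chances. The omission allowed in 7.3.6 works in the same direction. A volume where OFF leaks goes on to ON and can show an apparent benefit. A volume where OFF is dry may never be tested ON, so the opposite pair (dry OFF, leaking ON) can go unobserved.

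What is at stake is a primary comparison in at most 15 subjects. Section 10 says that the results may be used to design a powered study, and 11.9 plans publication. A few chance improvers could change the picture that the next study is built on.

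**Working it through.** The plan states no figure to reproduce: there is no power calculation, leak probability, number of tries or SD. The check asks what the testing rules do when stimulation has no effect. **Every p, k and SD below is an assumption.**

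**Step 1: independent tries.** Let p be the leak chance per test, the same OFF and ON. A dry OFF test is repeated up to k tries in total, and ON is tested once. The OFF leak rate is 1 - (1 - p)^k and the ON rate is p.

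| p | k | OFF leak rate | ON | Excess (points) |
|---|---|---|---|---|
| 0.3 | 1 | 0.300 | 0.30 | 0 |
| 0.3 | 2 | 1 - 0.7^2 = 0.510 | 0.30 | 21 |
| 0.3 | 3 | 1 - 0.7^3 = 0.657 | 0.30 | 36 |
| 0.5 | 2 | 1 - 0.5^2 = 0.750 | 0.50 | 25 |
| 0.5 | 3 | 1 - 0.5^3 = 0.875 | 0.50 | 38 |

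**Step 2: subjects differ.** Repeat tries in one woman are not independent, so step 1 overstates the gain. A simulation of 400,000 subjects used a leak threshold with SD 20 between and 15 within subjects, a provocation pressure with SD 15, and both centred at 100, so that p is 50% on average.

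- 2 OFF tries: 67.2% against 50.0% ON, an excess of about 17 points.
- 3 OFF tries: 75.7% against 50.0%, an excess of about 26 points.
- Analytic check for 2 tries: the correlation between tries is 20^2/(20^2 + 15^2 + 15^2) = 400/850 = 0.471. Both leak with probability 1/4 + arcsin(0.471)/(2π) = 0.328. At least one leaks with probability 0.5 + 0.5 - 0.328 = 0.672, which agrees.

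**Step 3: the omission in 7.3.6.** In the same simulation, scaled to 15 subjects with one volume each:

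| OFF tries (ON once) | OFF leaks, ON dry | OFF dry, ON leaks |
|---|---|---|
| 1 | 2.6 | 2.6 |
| 2 | 3.9 | 1.3 |
| 3 | 4.6 | 0.8 |

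The last column is seen only if ON is tested after a dry OFF. If ON is always left out there, only the middle column is observed. The omission alone therefore tilts the comparison, even with a single OFF try.

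**Step 4: equal attempts, ON always tested.** With 2 tries each, 67.3% leak OFF and 67.1% ON, with 2.1 apparent improvers and 2.0 apparent worseners of 15. With 3 tries each, 75.8% leak in both states, with 1.6 and 1.6. The tilt disappears.

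This result takes the number of attempts as fixed beforehand. If ON only copies a number set by when OFF first leaked, some tilt remains. With p = 0.5 and up to 2 independent tries, OFF leaks in 75%. ON gets one try half the time and two tries half the time: 0.5 × 0.50 + 0.5 × 0.75 = 62.5%. The excess falls from 25 to 12.5 points but not to zero.

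**The case against.** **The sentence in 6.3 may contain a slip.** Step 7.3.6 describes the ON test as a repeat of the LPP assessment and makes it optional after a dry OFF. If the first OFF in the 6.3 sentence is meant as ON, the two sections agree and the named OFF-repeat trigger falls. This is a fair reading and only the sponsor can settle it. The omission in 7.3.6, the open-ended repeats in note C and the live input would remain.

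**ON repeats are allowed.** Note C covers both states, and 7.3.6 allows more than one manoeuvre. So unequal testing is possible, not certain. Permission is not parity, however, and no rule says which reading counts.

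**The illustration is not on the endpoint's scale.** It concerns leak or no leak, while LPP is a pressure. That stands. The direction carries over because a dry test yields no leak pressure, so the repeats and omissions decide which OFF-ON pairs exist.

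**This is an exploratory study without tests.** There is no type I error to inflate, but a descriptive estimate can still be biased.

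**A reader might infer that the funder steers the result in its own favour.** The documents do not support that. Its role is advisory, participants may refuse its presence, remote attendance is by audio headset, and nothing says which results it can see. Notes C and D give the investigator the same freedom, so the problem exists without the funder.

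**A reader might also infer that volumes can be picked to flatter stimulation.** OFF and ON share each volume, and the volume is reached before its own results exist. Volume choice alone has no fixed direction.

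**Conclusion.** The point holds as a gap in the testing and analysis rules. As written, the plan allows the number of OFF attempts, and whether ON is tested at all, to depend on the OFF result. Either can favour stimulation when it has no effect, whoever proposes the repeat.

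The direction follows from the text, provided that OFF gets more attempts than ON or that ON is skipped after dry OFF tests. The size does not follow from the text. The figures of 21-38 points (independent tries, p of 30-50%, one or two extra OFF tries) and about 17-26 points (assumed SDs, 50% average leak chance) are illustrations. It would be wrong to read them as a forecast of bias in the reported LPP change. If the 6.3 sentence is a slip, the OFF-repeat figures apply only to repeats made under note C, and the omission in 7.3.6 becomes the main issue.

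**What to change.** 1. **Reconcile 6.3 with 7.3.6.** State whether the decision after a dry OFF test is to repeat OFF or to go on to ON.
2. **Match the attempts.** For the LPP comparison, use the same number of OFF and ON attempts at each volume analysed, including volumes where OFF was dry, unless a stopping reason already in 7.3.8 applies. Preferably set the number before the first OFF attempt at that volume, because matching afterwards reduces the tilt without fully removing it. Report separately the dry OFF volumes where ON was not tested.
3. **Record and log.** Enter the planned volumes on the CRF before infusion. Log every added volume or repeat, with its reason and who suggested it.
4. **Add an analysis rule to 10.1.** State one rule, the same for OFF and ON, for which attempt is analysed. Show unmatched extra attempts separately as exploratory.

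Restricting the comparison to first assessments is not advised. It would discard LPP values obtained on a repeat and would leave the omission in 7.3.6 in place.

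The cost is short wording in 6.3, 7.3 and 10.1, one CRF log, and some added ON tests and visit time within the existing limits of note B. The funder may still attend, and extra readings remain possible.

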6.4 End of Study Definition

The end of the study is defined as completion of Visit 3: Follow-Up Phone Call.

## 6.5 Table of Events

Activities	Visit 1: Screening and Enrollment Phone visit	Visit 2: Stimulation Visit Within 4 weeks of Visit 1	Visit 3: Follow-Up Phone Call 1 week +/- 2 days from Visit 2
Phone Consent	X		
Eligibility	X		
Medical History	X		
Urinary Incontinence History	X		
Neurostimulator Data	X		
Full Informed Consent		X	
Urinalysis		X	
Pregnancy Test 		X 	
Urodynamic Equipment Setting		X	
Stimulation Setting/Programming		X	
Antibiotic		X	
Urodynamic test with & without acute PNS		X	
UPP (optional)		X	
Adverse Event Assessment		X	X
Study Exit			X

For women of childbearing potential

## 7 Study Intervention Description

## 7.1 Study test equipment placement & setting

- 7.1.1 An oral antibiotic will be administered to the patient prior to UDT to reduce the risk of infection. The patient will receive either nitrofurantoin (100mg) or Bactrim Double Strength (80mg Trimethoprim/400mg sulfamethoxazole). Which antibiotic is prescribed will be based on patient known drug allergies and investigator determination.
- 7.1.2 Set up the urodynamic machine equipment per site's UDT operation procedure protocol.
- 7.1.3 Perform setup calibration to confirm proper UDT system function per institution practices. The subject will be asked to perform Valsalva and coughing to establish baseline pressure levels that the physician will intend to achieve during the study.
- 7.1.4 The neurostimulator's physician programmer will be used to program the implanted pulse generator deliver stimulation to the pudendal nerve via the implanted neurostimulator leads.

Note: For the testing, patient may be placed in a reclined, seated or standing position.

## 7.2 Acute Pudendal Nerve Stimulation (PNS) Setting

- 7.2.1 For the acute stimulation setting, the existing settings may be utilized or other settings within the range approved for use. Gradually increase amplitude and record urethral pressure and

amplitude per investigator.

7.2.2 Continue to increase amplitude progressively until discomfort noted and then reduce incrementally to the last acceptable level to the subject.

7.2.3 Per investigator, the electrode configuration and stimulation parameters may be changed as needed and 7.2.1-7.2.2 repeated.

7.2.4 Turn stimulation off.

### 7.3 Determine Leak Point Pressure Without and With Stimulation

7.3.1 Move the subject into a sitting or other position as per clinician.

7.3.2 Ensure acute stimulation parameters are set as determined in 7.1.4, above, so that the stimulation pulse train will be delivered continuously when manually turned on. The stimulation will be manually turned off for the infusion delivery periods.

7.3.3 Adjust the urodynamic system to infuse saline at 50 mL, 100mL or increments per investigator at a 50 mL/min infusion rate per physician's discretion.

7.3.4 Start the urodynamic saline infusion into the bladder until the first volume is reached (recommended at either 50mL, 100mL or per investigator) and pause the infusion.

7.3.5 Observe for urinary leakage while patient performs one or more coughs or Valsalva maneuvers with stimulation off to assess LPP.

7.3.6 Turn on stimulation per 7.1.4 and repeat the LPP assessment, using one or more coughs or Valsalva maneuvers as confirmation. Turn off stimulation. Note: This step may be omitted if no leak is observed in 7.3.5 or per physician's discretion.

7.3.7 Continue the urodynamic saline infusion (end the infusion pause mode) and fill the bladder to the next assessment point and stop infusion. Repeat the LPP with stimulation off, and then with stimulation on per 7.3.5 above 7.3.6.

7.3.8 Continue performing Valsalva and forceful coughs at additional bladder volume intervals without and with stimulation (steps) until patient has strong desire to void, bladder reaches major detrusor instability, patient has significant leakage (more than drops), patient has discomfort or any other reason per PI.

#### NOTES:

- A. The stimulation will be manually turned off while filling the bladder to the subsequent measuring point and for the off-stimulation LPP assessment. Stimulation is turned on only when the LPP assessments with stimulation are conducted.
- B. The stimulated periods shall not continue for more than approximately 60 seconds with no less than approximately 60 seconds of rest between stimulation periods.
- C. LPP assessment with or without stimulation may be repeated per PI discretion. Stimulation settings may be changed during the LPP assessment or before a repeat assessment.
- D. Bladder fill-in (infusion) rate and LPP assessment points (bladder volumes) are per physician discretion, UDT standard operation protocol and subject's UI profile.
- E. Infusion of saline to compensate for significant leakage as needed will be completed at PI discretion.

**7.4 Conduct UPP (Urethral Pressure Profile), Optional**

*Complete prior to filling bladder during UDT, and again when the bladder is filled to the point where the patient expresses a strong urge to urinate.*

- 7.4.1 The subject remains in a reclined, seated position or per investigator.
- 7.4.2 Connect the UPP catheter to the automatic indexing arm and adjust the traverse rate to 1/3 mm/sec. As an alternative, the UPP catheter may be withdrawn manually without the use of an automatic indexing arm: In this case, the steps of 1.0 cm or as per PI shall be achieved by using a reference mark on the catheter and annotating the urodynamic pressure recording correspondingly.
- 7.4.3 Ensure that the Pudendal neurostimulator is off.
- 7.4.4 Begin with the catheter placed such that the pressure sensitive portion is initially just inside the bladder. Complete 3 slow pulls.
- 7.4.5 Turn on stimulation per 7.2 and repeat the 3 UPP pulls as above
- 7.4.6 Once having completed the UPP turn off stimulation.

Note: UPP recording may be repeated per physician's discretion

**7.5 End of Test**

- 7.5.1 Remove all testing equipment (i.e. catheters, electrode pads)
- 7.5.2 Record any complication and adverse events
- 7.5.3 Discharge subject

**7.6 Concomitant Therapy**

No concomitant therapies are allowed during the urodynamic test procedure.

**8 Risk/Benefit Assessment**

This is an early feasibility study utilizing commercially released, market approved devices. Both the UDT system (Laborie, Sweden) and the implantable neurostimulator (Medtronic, USA) have been approved by the FDA for their respective indications. The study does not include any invasive nor experimental interventions/treatment. This study is considered low risk since the subjects that will be enrolled already have an implanted pudendal nerve stimulator and have already incurred the risks of the implantation procedure and the initial neurostimulation treatment as detailed in the neurostimulator manual. In addition, all the equipment needed for the study such as the urodynamic testing system are FDA regulated and used as standard of clinical testing in urology.

---

<https://www.medtronic.com/us-en/healthcare-professionals/products/urology/sacral-neuromodulation-systems/interstim-ii/indications-safety-warnings.html>

## 8.1 Known Potential Risks

Potential risks and harms are listed below in alphabetical order. These potential risks were identified consistent with Beaumont practices in research using urodynamic testing and electrical stimulation.

### 8.1.1 Potential Risks Associated with Urodynamic Test

The risks in this category are related to those of Urodynamic Testing. The estimated probability of these risks occurring is Less Frequent (occurring more than 1% but less than 10% of the time):

- Abrasion to rectum from rectal manometry catheter
- Abrasion to urethra from urethral catheter
- Anxiety
- Discomfort or pain during catheter insertion
- Mild cramping
- Minor bleeding
- Skin irritation (skin electrode adhesive)
- Temporary inability to urinate
- Urinary Tract Infection (UTI)

### 8.1.2 Potential Risks Associated with use of an antibiotic

Less Frequent (occurring more than 1% but less than 10% of the time):

- Diarrhea
- Nausea and vomiting
- Cramping

Rare (occurring less than 1% of the time):

- Headache
- Itching
- Rash
- Allergic reaction

### 8.1.3 Potential Risks Associated with Acute Pudendal Nerve Stimulation

The harms in this category only include those related to changing the device settings to deliver stimulation in a slightly different way that is still within the allowable ranges of the approved neurostimulator device. The differences in stimulation settings may include greater amplitude, different pulse width, frequency and different electrode configuration. The risks associated with the implanted stimulation system already exist in these patients since they were already implanted for the current indicated PNS treatment and the incremental risk incurred due to participation in the study is only due to the temporarily changed stimulation settings.

The incremental risks a subject may experience during the study procedure due to adjustment of the electrostimulation parameters and the delivery of acute vs. continuous PNS are alphabetically identified below. The estimated probability of these risks occurring is More Frequent (occurring more than 10% of the time):

- Temporary discomfort due to high level of stimulation
- Temporary dysesthesia (abnormal sensation)

- Temporary pain

The incremental risks a subject may experience after the conclusion of the study procedure due to adjustment of the electrostimulation parameters and the delivery of acute vs. continuous PNS are alphabetically identified below. The estimated probability of these risks occurring is Rare (occurring less than 1% of the time):

- Discomfort due to high level of stimulation
- Dysesthesia (abnormal sensation)
- Pain

## 8.2 Known Potential Benefits

There are no proven major short- or long-term benefits anticipated for the study subjects or society in general. Study subjects may learn more details regarding the nature of their urinary function. From a societal perspective, the data generated from these studies may prove to be essential foundational learning that may support progression toward an effective treatment for stress and mixed urinary incontinence.

